16.31 Primary Endpoint

- 16.311 The primary endpoint of this trial is the 12-month overall survival rate. This endpoint has been described as a binomial endpoint of success and failure, therefore patients lost to follow-up (eg, progressed/recurred, refusing further study participation, etc) prior to the time necessary for the binomial endpoint (eg, 12 months) will be defined as failure. All patients meeting the eligibility criteria who have signed a consent form and have begun treatment will be considered evaluable for the primary endpoint. All eligible patients will be followed until death or a minimum of 2 years.
- 16.312 Estimation: The proportion of successes will be estimated by the number of successes divided by the total number of evaluable patients. Confidence intervals for the true success proportion will be calculated.
- 16.313 Over Accrual: If more than the target number of patients are accrued, the additional patients will not be used to evaluate the stopping rule or used in any decision making processes; however, they will be included in final point estimates and confidence intervals.

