7.4 Criteria for Treatment Discontinuation

- Patients who develop PD/recurrent disease while receiving therapy at the time of response assessments will be discontinued from active study treatment and go off protocol;
- Grade 3 or 4 toxicity requiring break from treatment and inability to re-initiate treatments with a ≥ 28 day delay;
- Completion of 12 months of therapy.

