13.0 Treatment/Follow-up Decision at Evaluation of Patient

- 13.1 Patients who are CR, PR, or SD will continue treatment per protocol.
- 13.2 Patients who develop PD while receiving therapy will go to the event-monitoring phase.
- 13.3 Patients who go off protocol treatment for reasons other than PD will go to the event-monitoring phase per Section 18.0.
- 13.4 Patients who develop non-CNS PD at any time should go to event monitoring.
- 13.5 A patient is deemed *ineligible* if after registration, it is determined that at the time of registration, the patient did not satisfy each and every eligibility criteria for study entry. The patient may continue treatment off-protocol at the discretion of the physician as long as there are no safety concerns, and the patient was properly registered. The patient will go directly to the event-monitoring phase of the study (or off study, if applicable).
- If the patient received treatment, all data up until the point of confirmation of ineligibility must be submitted. Event monitoring will be required per Section 18.0 of the protocol.
 - If the patient never received treatment, on-study material must be submitted. Event monitoring will be required per Section 18.0 of the protocol.
- 13.6 A patient is deemed a *major violation*, if protocol requirements regarding treatment in cycle 1 of the initial therapy are severely violated that evaluability for primary end point is questionable. All data up until the point of confirmation of a major violation must be submitted. The patient will go directly to the event-monitoring phase of the study. The patient may continue treatment off-protocol at the discretion of the physician as long as there are no safety concerns, and the patient was properly registered. Event monitoring will be required per Section 18.0 of the protocol.

- 13.7 A patient is deemed a cancel if he/she is removed from the study for any reason before any study treatment is given. On-study material and the End of Active Treatment/Cancel Notification Form must be submitted. The patient will go directly to the event-monitoring phase of the study, and event monitoring will be required per Section 18.0 of the protocol.

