16.0 Statistical Considerations and Methodology

- 16.1 Overview: This protocol will assess the efficacy of pazopanib in patients with non-clear cell metastatic renal cancer using a one-stage phase II study design.
- 16.11 Primary Endpoint: The primary endpoint of this trial is the 12-month overall survival rate. A “12-month overall survivor” will be considered synonymous with “success”, unless otherwise specified. A patient is considered to be a 12-month survivor if the patient lives 12 months from registration (note, all deaths prior to 12 months, regardless of cause, will be considered a failure). All patients meeting the eligibility criteria who have signed a consent form and have begun treatment will be evaluable for the primary endpoint. All eligible patients will be followed until death or a minimum of 2 years.
- 16.2 Statistical Design:
- 16.21 Decision Rule: The largest success proportion where the proposed treatment regimen would be considered ineffective in this population is 55%, and the smallest success proportion that would warrant subsequent studies with the proposed regimen in this patient population is 75%. The one-stage design based on properties of the binomial distribution uses 39 patients to test the null hypothesis that the true success proportion in a given patient population is at most 55%.
- 16.22 Sample Size: There will be 35 evaluable patients accrued onto this study unless undue toxicity is encountered. We anticipate accruing an additional 4 patients to account for ineligibility, cancellation, major treatment violation, or other reasons.
- 16.23 Accrual Time and Study Duration: The anticipated accrual rate is approximately 1-2 patients per month, based on the incidence of tumor type and the potential to accrue at Mayo Clinic sites (Mayo Clinic Rochester, Mayo Clinic Florida and Mayo Clinic Arizona). Therefore, the accrual period for this phase II study is expected to be 24 months. The final analysis can begin approximately 36 months after the trial begins, i.e. as soon as the last patient has been observed for 12 months.

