- 16.24 Power and Significance Level: The null 12-month overall survival rate of 55% is based on the Kaplan-Meier estimate of 12-month survival from the Mayo Clinic Nephrectomy database (Leibovich, Lohse et al.). Assuming that the number of successes is binomially distributed and the significance level is ≤ 0.10 , we are required to accrue evaluable 35 patients to achieve an 80% power under the alternative hypothesis of a 75% success proportion.
- 16.3 Analysis Plan: The analysis for this trial will commence at the time all patients have become evaluable for the primary endpoint. Such a decision will be made by the Statistician and Study Chair, in accord with standard operating procedures, availability of data for secondary endpoints, and the level of data maturity.

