- If 4 or more patients in the first 15 treated patients or anytime thereafter more than 25% of patients experience a \geq grade 4 or higher adverse event, except for hypertension, diarrhea, and abnormal liver function tests, accrual will be temporarily suspended.

We note that we will review grade 4 and 5 adverse events deemed “unrelated” or “unlikely to be related”, to verify their attribution and to monitor the emergence of a previously unrecognized treatment-related adverse event.

16.5 Results Reporting on ClinicalTrials.gov: At study activation, this study will have been registered within the “ClinicalTrials.gov” website. The primary and secondary endpoints (ie, “Outcome Measures”) along with other required information for this study will be reported on ClinicalTrials.gov. For purposes of timing of the Results Reporting, the initial estimated completion date for the Primary Endpoint of this study is 36 months after the study opens to accrual. The definition of “Primary Endpoint Completion Date” (PECD) for this study is at the time the last patient registered has been followed for at least 12 months overall survival status.

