18.0 Records and Data Collection Procedures

18.1 Submission Timetable

Initial Material(s) -

CRF	Active-Monitoring Phase (Compliance with Test Schedule Section 4.0)
On-Study Form ¹	≤ 2 weeks after registration
Adverse Events: Baseline	
RECIST Measurements: Baseline	
Specimen Submission: Blood (see Section 14.0)	
Specimen Submission: Urine (see Section 14.0)	
Laboratory Tests and Results	
Concomitant Medication Form	
Patient Status: Baseline	
Off Treatment ²	Submit ≤ 2 weeks after registration if withdrawal/refusal occurs prior to beginning protocol therapy

1. On-Study: Prior Surgery, On-Study Prior Radiation, and On-Study Prior Systemic Therapy will be added as needed.
2. Added if needed based on the responses on the Patient Status: Baseline form

Central Pathology Review Material(s) -

CRF	Active-Monitoring Phase (Compliance with Test Schedule Section 4.0)
Pathology Materials (this is for central review, eligibility, etc.)	Submit ≤30 days after registration

Test Schedule Material(s) -

CRF	Active-Monitoring Phase (Compliance with Test Schedule Section 4.0)	
	At each evaluation during treatment	At end of treatment
Treatment (Intervention)	X ¹	X
Adverse Events: Solicited	X	X
RECIST Measurement ² s	X	X
Specimen Submission: Blood	X (see Section 14.0)	
Specimen Submission: Urine	X (see Section 14.0)	
Laboratory Tests and Results	X	X
Concomitant Medications	X	X
Patient Status: Treatment	X	
Off Treatment ²		X
Notification Form – Grade 4 or 5 Non-AER Reportable Events/Hospitalization Form	At each occurrence (see Section 10.0)	
ADR/AER	At each occurrence (see Section 10.0)	

1. Complete at each evaluation during Active Treatment (see Section 4.0).
2. Added if needed based on the responses on the Patient Status: Treatment form

Follow-up Material(s) -

CRF	Survival Follow-up Phase¹				
	q.  3  months until PD	At PD ¹	After PD q.  6  mos.	Death	New Primary
Patient Status: Survival Follow-up ¹	X ²	X ²	X	X	At each occurrence

1. If a patient is still alive 2 years after registration, no further follow-up is required.
2. Submit copy of documentation of response or progression to the MCCC Operations Office, Attention: QAS for MC1152

- 18.2 Patient identification labels will be produced for each patient entry. The labels are produced for use on the data forms and will be mailed to the co-sponsors/participants twice. Additional labels may be obtained by directly calling the Mayo Clinic Cancer Center (MCCC) Registration Office [REDACTED].

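### Section 16.311 lets progression or refusal count as failure on 12-month overall survival, so a patient known to be alive at 12 months can be scored either way

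*Combined protocol and SAP*

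**What the plan says.** Section 16.11 sets the endpoint: "The primary endpoint of this trial is the 12-month overall survival rate". It defines success by survival alone: "A patient is considered to be a 12-month survivor if the patient lives 12 months from registration". The only failure it names is death before 12 months, from any cause. It also treats survivor and success as the same thing unless another provision says otherwise.

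Section 16.311 adds a second route to failure. Its wording is "therefore patients lost to follow-up (eg, progressed/recurred, refusing further study participation, etc) prior to the time necessary for the binomial endpoint", and it classes these patients as failures.

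Other sections bear on what happens after progression:

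- Section 13.2: "Patients who develop PD while receiving therapy will go to the event-monitoring phase". Section 13.3 does the same for patients who stop treatment for other reasons.
- Section 18.1 requires a survival form at progression and every 6 months afterwards. Its footnote reads "If a patient is still alive 2 years after registration, no further follow-up is required".
- Sections 16.11 and 16.311 both keep all eligible patients under follow-up to death or for at least 2 years.
- Section 16.5 places primary completion at the point when "the last patient registered has been followed for at least 12 months overall survival status".
- Section 16.322 makes progression an event in the secondary progression-free survival (PFS) endpoint.
- Section 7.4 says that patients who progress on therapy "will be discontinued from active study treatment and go off protocol".

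The 55% null is, per Section 16.24, "based on the Kaplan-Meier estimate of 12-month survival from the Mayo Clinic Nephrectomy database".

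**The concern.** The parenthesis in 16.311 presents progression and refusal as instances of loss to follow-up. Under this protocol neither one ends survival follow-up, so vital status at 12 months should normally be known for these patients. Nothing in the text says that a patient known to be alive at 12 months is a success despite earlier progression or refusal. Two analysts could score the same patient differently on the primary endpoint, and each could point to a section in support.

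The literal reading also breaks the comparison with the null. The historical 55% counts deaths only. If the trial counts deaths plus some progressions and refusals, the observed proportion and the null measure different quantities. Every survivor scored as a failure lowers the observed proportion while the benchmark stays fixed. The error therefore runs toward rejecting an active drug, and the type I error falls below its planned level.

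**Working it through.** **Inputs from the documents.** Null p0 = 0.55 and alternative p1 = 0.75 (16.21); significance level at most 0.10, power 80%, 35 evaluable patients (16.24). Section 16.21 refers to 39 patients, so both sizes are shown. No success cut-off is stated.

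**Assumed inputs.** The share f of true 12-month survivors who would be scored as failures, and the median PFS. The documents give neither for this drug in this population.

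**Step 1: the plan's own figure.** The normal approximation is n = [(z_α√(p0(1−p0)) + z_β√(p1(1−p1))) / (p1−p0)]². A two-sided level of 0.10 gives 34.97, rounded up to 35, which matches 16.24. A one-sided level of 0.10 gives 25.1, rounded up to 26.

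**Step 2: exact rules.** Take the smallest r with P(X ≥ r | 0.55) ≤ 0.10.

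| n | r | type I error | power at 75% |
|---|---|---|---|
| 35 | 24 | 0.073 | 85.8% |
| 39 | 26 | 0.095 | 91.4% |

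Lowering r by one breaks the limit (0.134 at n=35, 0.163 at n=39).

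**Step 3: a share f of survivors mis-scored.** The success probability becomes p(1−f). For example, f = 10% gives 0.75 × 0.90 = 0.675 under the alternative and 0.55 × 0.90 = 0.495 under the null.

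| f (assumed) | power, n=35 | type I, n=35 | power, n=39 | type I, n=39 |
|---|---|---|---|---|
| 2% | 80.5% | 0.057 | 87.3% | 0.074 |
| 5% | 71.1% | 0.038 | 79.3% | 0.049 |
| 10% | 52.6% | 0.018 | 61.8% | 0.023 |
| 15% | 34.3% | 0.008 | 42.2% | 0.010 |

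Power reaches 80% at p = 0.7336 for n=35, so f = 1 − 0.7336/0.75 = 2.2%. For n=39 it is p = 0.7142, so f = 4.8%. At f = 1 − 0.55/0.75 = 26.7%, the effective rate under the alternative equals the null.

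**Step 4: the same in patients.** If k survivors are scored as failures, the trial needs r + k true survivors, so power is P(X ≥ r+k | 0.75). For k = 1, 2, 3 this is 75.8%, 62.6% and 47.4% at n=35, and about 85%, 75% and 62% at n=39.

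**Step 5: every progression counts.** The success probability is then PFS at 12 months. Assuming exponential PFS, p = 0.5^(12/median).

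| median PFS (assumed) | p | power, n=35 | power, n=39 |
|---|---|---|---|
| 7.1 months | 0.310 | about 0% | about 0% |
| 12 months | 0.500 | 2% | 3% |
| 18 months | 0.630 | 31% | 38% |
| 24 months | 0.707 | 69% | 77% |

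Holding 80% power would need a median PFS of about 26.9 months (n=35) or 24.7 months (n=39). The 7.1 months comes from Section 1.3, for a different regimen in collecting duct tumors. It serves only as the low end of the range.

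**The case against.** The best reply is that loss to follow-up is the operative condition and the parenthesis merely lists reasons why a patient might be lost. A patient known to be alive at month 12 was not lost, so 16.311 would not reach that patient. The surrounding text favors this reading: 16.311 itself restates the survival endpoint and the 2-year follow-up, 13.2 and 18.1 keep progressed patients under observation, and progression has its own endpoint in 16.322. Section 7.4 sits under treatment discontinuation and need not mean that survival tracking stops. Scoring patients of truly unknown status as failures is an accepted conservative rule. The mis-scoring rates are assumed, and the bias does not favor the drug.

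Much of this stands. The narrow reading is plausible and probably intended, and under it the rule is no error. But 16.311 does not say so. It names progression itself as an instance of loss, and 16.11 leaves room for a later provision to override its equation of survivor with success. Refusal is a fair reason for unknown status, but it still should not override status that is known. The slack between 85.8% and 80% power at n=35 does not survive one mis-scored survivor.

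**Conclusion.** The concern holds. As written, the primary endpoint has two scoring rules that can disagree for a patient known to be alive at 12 months. That the text allows both is certain. The size of the effect depends on how 16.311 is applied: none for patients of known status on the narrow reading, a loss from 85.8% to 75.8% power for a single mis-scored survivor at n=35, and near-total loss of power if every progression counts and median PFS is 12 months or less. These figures rest on exact cut-offs derived here, on assumed mis-scoring rates, and in the last case on exponential PFS. The direction does not depend on those assumptions: both power and type I error fall. With about 35 patients, one or two can decide the result, so the rule must be settled before analysis.

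**What to change.** In 16.311, remove progression/recurrence and refusal as grounds for failure. State that each evaluable patient is scored on actual vital status at 12 months from registration, whatever happened earlier regarding progression or participation. State that loss to follow-up counts as failure only when 12-month vital status cannot be determined. Keep the binomial test as the primary analysis and report how many patients had unknown status.

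Two additions would help but are not essential. One is a Kaplan-Meier estimate of 12-month survival as a sensitivity analysis, censoring patients of unknown status at the date last known alive. It may be biased upward if patients who progress and then disappear do worse, so it should not be primary. The other is a month-12 vital-status check by chart or telephone in the 18.1 table, because contact after progression is only every 6 months.

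The cost is two or three sentences, plus one extra analysis and minor data collection if the additions are taken up. No further patients are needed.

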16.32 Definitions and Analyses of Secondary Endpoints

- 16.321 A tumor response is defined to be a CR or PR noted as the objective status on 2 consecutive evaluations at least 8 weeks apart. Tumor response will be evaluated. All patients meeting the eligibility criteria who have signed a consent form and have begun treatment will be evaluable for response.
- 16.322 Progression-free survival is defined as the time from registration to the earliest date documentation of disease progression or death. Kaplan-Meier curve will be used to estimate progression-free survival time.
- 16.323 Adverse events: All eligible patients that have initiated treatment will be considered evaluable for assessing adverse event rate(s). The maximum grade for each type of adverse event will be recorded for each patient, and frequency tables will be reviewed to determine patterns. Additionally, the relationship of the adverse event(s) to the study treatment will be taken into consideration.
- 16.324 Observation Phase: Retreatment of patients who have relapsed will be left to the discretion of the treating physician. Statistical analysis of the observational phase data for these patients will be of a descriptive nature.

16.4 Data & Safety Monitoring:

16.41 The study chair(s) and the study statistician will review the study at least twice a year to identify accrual, adverse event, and any endpoint problems that might be developing. The Mayo Clinic Cancer Center (MCCC) Data Safety Monitoring Board (DSMB) is responsible for reviewing accrual and safety data for this trial at least twice a year, based on reports provided by the MCCC Statistical Office.

16.42 Adverse Event Stopping Rules: The stopping rules specified below are based on the knowledge available at study development. We note that the Adverse Event Stopping Rule may be adjusted in the event of either (1) the study re-opening to accrual or (2) at any time during the conduct of the trial and in consideration of newly acquired information regarding the adverse event profile of the treatment(s) under investigation. The study team may choose to suspend accrual because of unexpected adverse event profiles that have not crossed the specified rule below.

Accrual will be temporarily suspended to this study if at any time we observe events considered at least possibly related to study treatment (i.e. an adverse event with attribute specified as “possible”, “probable”, or “definite”) that satisfy the following:

- If 4 or more patients in the first 15 treated patients or anytime thereafter more than 25% of patients experience a \geq grade 4 or higher adverse event, except for hypertension, diarrhea, and abnormal liver function tests, accrual will be temporarily suspended.

We note that we will review grade 4 and 5 adverse events deemed “unrelated” or “unlikely to be related”, to verify their attribution and to monitor the emergence of a previously unrecognized treatment-related adverse event.

16.5 Results Reporting on ClinicalTrials.gov: At study activation, this study will have been registered within the “ClinicalTrials.gov” website. The primary and secondary endpoints (ie, “Outcome Measures”) along with other required information for this study will be reported on ClinicalTrials.gov. For purposes of timing of the Results Reporting, the initial estimated completion date for the Primary Endpoint of this study is 36 months after the study opens to accrual. The definition of “Primary Endpoint Completion Date” (PECD) for this study is at the time the last patient registered has been followed for at least 12 months overall survival status.

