CT scan of chest, abdomen or pelvis, MRI, etc		X ^R			X ⁷	
Bone Scan					X ⁵	
EKG		X ^R	X			
Medication Diary			X ³			

1. SGOT, SGPT, total bili, Na, K, Cl, CO₂, BUN, creatinine, LDH, hemoglobin, calcium, albumin, total protein, magnesium, phosphorus and alkaline phosphatase.
2. For women of childbearing potential, ≤7 days prior to registration.
3. The diary must begin the day the patient starts taking the medication and must be completed per protocol and returned to the treating institution OR compliance must be documented in the medical record by any member of the care team.
4. +/- 3 days
5. If applicable
6. Research funded, cycles 1 and 2 only
7. Use the same method throughout the study. Follow-up scans to be performed every other cycle (8 weeks). Repeat measurements are required 8 weeks following an objective Response. See Section 11.0 for full RECIST criteria.
8. Every 4 months while on study, sooner should clinical symptoms indicate. These follow-up echocardiograms will coincide with restaging visits.
9. SGOT, SGPT, total bili, only and can be done at study site or locally and faxed.
- R Research funded (see Section 19.0)

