7.12 Dosage and Administration

Administration of pazopanib with a high-fat or low-fat meal results in an approximately 2-fold increase in area under the plasma drug concentration curve (AUC) and maximum observed plasma drug concentration (C_{max}).

Pazopanib should be taken orally without food at least one hour before or two hours after a meal. The tablets should be swallowed whole and must not be crushed or broken. The time of day the tablets are taken should be relatively constant.

If a dose is missed, the subject should take the dose as soon as possible, but only if there are 12 or more hours remaining before the next dose is due. If the next dose is due in less than 12 hours, the subject should skip the missed dose and take the next dose as scheduled.

If vomiting occurs after taking pazopanib, the subject should not take a replacement dose on that day. The subject should resume taking pazopanib at the next scheduled dose on the following day. If vomiting persists, the subject should be instructed to notify the investigator.

As a general rule, if dose reduction of pazopanib is necessary, the dose should be reduced stepwise by 200 mg at each step, and the subject should be monitored for approximately 10 to 14 days at each dose level. If toxicity does not abate during this monitoring time, the medication may need to be interrupted and/or the dose further decreased with continued monitoring for an additional 10-14 days at each dose level, and so on.

If the toxicity has abated with reduction of the dose and dose re-escalation is considered safe by the investigator, the dose can then be increased step-wise back to the pre-event dose (in 200 mg increments, after monitoring for 10-14 days at each dose level to ensure that toxicity did not recur or worsen).

If a subject's treatment has been interrupted for more than 21 days, the Investigator must contact the Study Physician to review the subject's condition in order to resume the treatment.

- 7.2 Patients can be instructed in administration techniques and granted treatment independence with nursing staff approval.
- 7.3 For this protocol, the patient must return to Mayo Rochester, Florida, or Arizona for evaluation at least every 28 days (+/- 3 days).

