11.0 Treatment Evaluation Using RECIST Guideline

NOTE: This study uses protocol RECIST v1.1 template dated 2/16/2011. See the footnote for the table regarding measurable disease in Section 11.44, as it pertains to data collection and analysis.

Response and progression will be evaluated in this study using the new international criteria proposed by the revised Response Evaluation Criteria in Solid Tumors (RECIST) guidelines (version 1.1) Changes in the largest diameter (unidimensional measurement) of the tumor lesions and the short axis measurements in the case of lymph nodes are used in the RECIST guideline.

- 11.1 Schedule of Evaluations: For the purposes of this study, patients should be reevaluated every 8 weeks. In addition to a baseline scan, confirmatory scans should also be obtained 8 weeks following initial documentation of objective response.
- 11.2 Definitions of Measurable and Non-Measurable Disease

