 - a. Negative FDG-PET at baseline with a positive FDG-PET at follow-up is a sign of PD based on a new lesion.
 - b. No FDG-PET at baseline and a positive FDG-PET at follow-up:
 - i. If the positive FDG-PET at follow-up corresponds to a new site of disease confirmed by CT, this is PD.
 - ii. If the positive FDG-PET at follow-up is not confirmed as a new site of disease on CT at the same evaluation, additional follow-up CT scans (i.e., additional follow-up scans at least 4 weeks later) are needed to determine if there is truly progression occurring at that site. In this situation, the date of PD will be the date of the initial abnormal PDG-PET scan.
 - iii. If the positive FDG-PET at follow-up corresponds to a pre-existing site of disease on CT that is not progressing on the basis of the anatomic images, it is not classified as PD.

11.33 Measurement at Follow-up Evaluation:

- In the case of stable disease (SD), follow-up measurements must have met the SD criteria at least once after study entry at a minimum interval of 8 weeks (see Section 11.44).
- The cytological confirmation of the neoplastic origin of any effusion that appears or worsens during treatment when the measurable tumor has met criteria for response or stable disease is mandatory to differentiate between response or stable disease (an effusion may be a side effect of the treatment) and progressive disease.
- Cytologic and histologic techniques can be used to differentiate between PR and CR in rare cases (e.g., residual lesions in tumor types such as germ cell tumors, where known residual benign tumors can remain.)

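### The response definition needs two scans at least 8 weeks apart, but scans are scheduled exactly 8 weeks apart, so a slightly early confirming scan can void a response

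*Combined protocol and SAP*

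**What the plan says.** Section 16.321 defines a tumor response as CR or PR "noted as the objective status on 2 consecutive evaluations at least 8 weeks apart". It gives no tolerance below 8 weeks and does not say that a nominal 8-week visit counts.

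The schedule uses the same 8 weeks as its target:

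- Section 4.0, footnote 7: "Follow-up scans to be performed every other cycle (8 weeks). Repeat measurements are required 8 weeks following an objective Response".
- Section 11.1: "patients should be reevaluated every 8 weeks", and "confirmatory scans should also be obtained 8 weeks following initial documentation of objective response".
- Section 7.1 sets the cycle at 28 days.

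Cycle visits have a window. Footnote 4 of Section 4.0 allows 3 days either way and is marked on the column for Day 1 of every cycle. Section 7.3 has patients return "for evaluation at least every 28 days (+/- 3 days". CT/MRI sits in a different column, for every other cycle, under footnote 7, which states no window.

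**The concern.** When a minimum gap equals the planned gap, only on-time or late scans qualify. A scan that slips early fails, so ordinary calendar variation acts in one direction only: it can remove responses and cannot add them. Two patients with the same tumor measurements could be scored differently because one attended a day sooner.

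The rule also requires consecutive evaluations. If scans 1 and 2 are 55 days apart, scans 1 and 3 (about 112 days apart) cannot stand in for them, and a new adjacent pair must qualify. At stake is a downward bias in the response rate. If the rule stays as it is, someone will also have to decide how to score near-miss pairs once outcomes are known.

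**Working it through.** **The plan's own figure.** Two cycles × 28 days = 56 days = 8 weeks, so the stated scan interval reproduces. The margin over the 16.321 minimum is 56 − 56 = 0 days.

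**Assumption.** Each timing offset is a whole number of days from −3 to +3, independent of the others. The documents give no actual scan timing, and applying the visit window to scans is an inference.

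**Possible gaps under three timing models**

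- A. Both scans float around fixed calendar dates: gap = 56 + e₂ − e₁, range 50 to 62 days.
- B. The confirming scan is timed from the response scan: gap = 56 + e, range 53 to 59 days.
- C. Each of the two cycles may vary by 3 days: gap = 56 + a + b, range 50 to 62 days.

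**Response seen on exactly two scans, uniform offsets.** P(gap < 56) is 21/49 in A and C, and 3/7 in B. All equal 42.9%.

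**Same response, more visits on schedule.** Let p be the share of visits exactly on schedule, with the rest spread evenly over the other six days. Model A gives [1 − p² − (1 − p)²/6]/2, and model B gives (1 − p)/2.

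| p | Model A | Model B |
|---|---|---|
| 0.5 | 35.4% | 25% |
| 0.7 | 24.8% | 15% |
| 0.9 | 9.4% | 5% |

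**Response lasting k scans, uniform offsets.** It is lost only if every adjacent gap is short. Model A gives C(7,k)/7ᵏ, and models B and C give (3/7)ᵏ⁻¹.

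| Responding scans | Model A | Models B, C |
|---|---|---|
| 3 | 35/343 = 10.2% | 18.4% |
| 4 | 1.5% | 7.9% |
| 5 | 0.1% | 3.4% |

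**Scale.** Section 16.22 plans 35 evaluable patients. Section 1.2 cites response rates of 5% to 17% for related drugs in small retrospective series, used here only to set the scale.

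- Responders: 35 × 0.05 = 1.75, to 35 × 0.17 = 5.95.
- Worst case (every response on exactly two scans, uniform offsets): 1.75 × 3/7 = 0.75, to 5.95 × 3/7 = 2.55 uncounted.
- Reported rate in that case: 5% × 4/7 = 2.9%, to 17% × 4/7 = 9.7%.
- One lost responder moves the rate by 1/35 = 2.9 percentage points.

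**Checking candidate minimums.** The shortest gap with both scans inside the window is 56 − 6 = 50 days, so a 50-day minimum fails no on-schedule pair in any of the three models. A 53-day minimum would still fail 6/49 = 12.2% of pairs in model A.

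**The case against.** The strongest reply is that the rules do not formally conflict. The ±3 day window is written for Day 1 visits, and none is stated for scans. A confirming scan done at 8 weeks, as Sections 4.0 and 11.1 ask, satisfies 16.321, so a loss would come from conduct rather than from contradictory text. It is right that the window's use for scans is not stated. The inference is still reasonable, because footnote 8 of Section 4.0 ties follow-up echocardiograms to restaging visits, and Section 7.3 applies the window to return visits for evaluation. Even without a window the definition has no tolerance, and any early scan breaks it.

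The second reply is that the effect is modest. Uniform offsets are a pessimistic assumption. Treatment may last 12 months (Section 7.4), which allows about six scans, and a lasting response has several chances to qualify. Response has no target rate or decision rule, and the exact 95% interval for 4/35 runs from 3% to 27%, far wider than the likely shift. All of this stands, and it limits the size. It does not remove the problem for short responses, such as one followed by progression at the third scan. Nor does it help one first seen at week 40, which has a single on-treatment confirming pair.

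A reader might also infer that stable disease has the same fault, since Section 11.33 says "follow-up measurements must have met the SD criteria at least once after study entry at a minimum interval of 8 weeks". The documents do not support that. The 8 weeks there run from study entry, which Section 13.5 ties to registration, and Section 6.5 lets treatment start up to 14 days later. A scan 3 days early falls short only if treatment began within 2 days of registration. With start delay uniform over 0–14 days and offset uniform over ±3, that is 6/105, about 6%. A later scan can also satisfy the rule, and Section 16.32 defines no stable-disease endpoint.

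**Conclusion.** The point holds as a wording defect in a secondary endpoint. Applied literally, 16.321 rejects a response repeated at day 53, 54 or 55, although such a scan would be on schedule if the visit window covers scans. The bias is downward only.

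The 5–35% and 43% losses apply to responses seen on exactly two scans. The first assumes 50–90% of visits fall exactly on schedule, and the second assumes uniform offsets. Neither is a forecast, because actual timing is not in the documents. At most about 1 to 3 of 35 patients would be affected.

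Two stronger readings are not supported. One is that the plan will discard true responses. On-time and late pairs qualify, and longer responses usually qualify on a later pair, so this is a risk and not a certain result. The other takes the 11% in Section 1.2 as a true confirmed rate and projects the loss from it. That section calls it an overall response rate and does not say it was confirmed.

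Nothing here touches the 12-month survival endpoint, its decision, the sample size or the power.

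**What to change.** In 16.321, change the confirmation requirement to *2 consecutive scheduled evaluations (nominally 8 weeks, at least 50 days apart)*. In footnote 7 of Section 4.0, state that the ±3 day window applies to scans. Leave Section 11.33 as it is.

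This costs one sentence in each place, with no added scans or patients. The small downside is that a confirmation interval up to 6 days shorter than 8 weeks is accepted. The alternative is to keep the 8-week minimum and state that the confirming scan may not be done early. Either choice should be made before the response data are analyzed.

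While 16.321 is open, it should also be reconciled with objective 2.21. That objective places best response at the end of the first two cycles, whereas a response first seen then cannot be confirmed under 16.321 until about week 16. This is a separate matter from the timing margin.
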